9.3.3 Cycle ergometry

Cycle ergometry will be performed at the time points specified in [Section 1.1](#). Completion of the assessment may depend upon patient cooperation.

Cardiopulmonary status will be assessed using a stationary 1-wheeled cycle as an ergometer to measure a person's work output under controlled conditions. Patients will be asked to ride the cycle at increasing workload levels until they can no longer proceed. Patients will breathe through a tube connected to a 1-way valve for continuous measurements of oxygen (O₂) uptake, carbon dioxide (CO₂) output, and tidal volume throughout the test. Heart rate, respiratory rate, and digital O₂ saturation will also be continuously monitored. Steady-state levels for each workload will be calculated for O₂ uptake, CO₂ output, tidal volume, ventilation, and respiratory exchange ratio. The maximum workload achieved will be recorded and expressed as percent predicted. In addition, percent predicted maximum will be calculated for O₂ uptake, heart rate, and tidal volume. Note that cycle ergometry assessments must occur at the same time for each assessment (ie, ± 2 hours of the time of day of the first assessment).

Procedures for cycle ergometry assessments are detailed in the corresponding manual.

9.3.4 Efficacy biomarkers

Blood samples for efficacy biomarkers will be collected prior to infusion at the time points specified in [Section 1.1](#) through [Section 1.5](#). Biomarkers will include, but not be limited to, serum chitotriosidase, CCL-18.

Processing, storage, and shipment guidelines for samples to be sent to the sponsor are provided in the corresponding manual.

9.3.5 Bone disease assessments

Bone disease assessments will be obtained only for patients who previously participated in the DFI13412 study as specified in [Section 1.1](#) through [Section 1.5](#). Magnetic resonance imaging of the lumbar spine and both femurs will be used to determine bone marrow burden scores ([20](#), [21](#)). Dual-energy X-ray absorptiometry of the lumbar spine and both femurs will provide total BMD measurements, BMD T-scores, and Z-scores. The assessments may be performed on the same day as the spleen and liver volume MRIs.

All bone images will be sent to a central reviewer for blinded analysis of potential bone disease. See the corresponding manual for further details.

9.3.6 Bone biomarkers

Serum bone-specific alkaline phosphatase and C-telopeptide levels will be evaluated as indicated in [Section 1.1](#) through [Section 1.5](#).

9.3.7 Patient photographs

Photographs (eg, abdominal) will be taken as specified in [Section 1.1](#) through [Section 1.5](#) of patients who volunteer to provide visual context of the disease.

9.3.8 Pharmacokinetics

For both adult and pediatric patients, PK testing will only occur yearly for the first 5 years and upon the introduction of Process C(█) or Process C(█) at any time during the study. For Process C(█), if treatment is not interrupted, PK sample collection will take place at the patient's last infusion under the current manufacturing scale and at the first infusion Process C(█). For introduction of drug product from Process C(█), if treatment is not interrupted, PK sample collection will take place at the second infusion under Process C(█). In case reintroduction of olipudase alfa coincides with introduction of a drug product from Process C(█) or Process C(█), PK samples will be collected at the infusions at which patients receive their usual dose of olipudase alfa under the new process.

Blood samples for pediatric patients are drawn at different intervals than samples in adult patients ([Section 1.6](#), [Table 12](#) and [Table 11](#), respectively) and in different volumes ([Section 9.5](#)).

9.3.8.1 Pharmacokinetics handling procedure

Special procedures for collection, storage, and shipment are provided in the corresponding manual.

9.3.8.2 Bioanalytical method

Plasma will be separated from blood samples and analyzed for plasma concentrations of olipudase alfa using a validated enzyme-linked immunosorbent method.

9.3.8.3 Pharmacokinetic sampling and parameters in adults

9.3.8.3.1 Sampling time in adults

Pharmacokinetic sampling will occur at the time points listed in [Section 1.1](#) and [Section 1.6](#). Specific time points are detailed in [Table 11](#). If a patient receives only a partial infusion (eg, due to a safety concern), PK sampling will be repeated the next time the patient receives that dose. If a repeat is required, all PK time points will be repeated.

Windows around PK blood samples are ± 10 minutes for collection times less than 8 hours and ± 3 hours for collection times of 8 hours or longer post infusion.

Blood samples may be drawn for PK assessments using an indwelling catheter from an arm that is not used for dose administration. The exact time of dose administration (start and stop times of infusion), rate of infusion, and dose will be recorded along with exact sampling times.

If a manufacturing scale change occurs, serial blood samples for PK will be collected at all of the same time points with the last infusion of olipudase alfa produced at the original scale and with the first infusion of olipudase alfa produced at the new scale. For introduction of drug product from Process C(█), PK sample collection will only take place at the second infusion under Process C(█).

9.3.8.3.2 Number of pharmacokinetic samples in adults

[Table 14](#) shows the approximate number of plasma samples in adults.

Table 14 - Approximate number of plasma samples in adult patients

Collection	Number of samples
Yearly collection (5 years)	8
Change in manufacturing scale	
Last infusion on old scale	8
First infusion on new scale	8
Updated manufacturing process	
Second infusion on updated process	8
Total by patient	64

9.3.8.3.3 Pharmacokinetics parameters in adults

The following PK parameters will be calculated using noncompartmental methods from plasma olipudase alfa concentrations. The parameters will include, but may not be limited to, those listed in [Table 15](#).

Table 15 - List of pharmacokinetic parameters and definitions

Parameters	Drug/Analyte	Definition/Calculation
C_{max}	olipudase alfa	Maximum plasma concentration observed
C_{eoI}	olipudase alfa	Concentration at the end of infusion
t_{max}	olipudase alfa	Time to reach C_{max}
AUC_{last}	olipudase alfa	Area under the plasma concentration-versus-time curve calculated using the trapezoidal method from time zero to the real time
$AUC_{0-\infty}$	olipudase alfa	Area under the plasma concentration-versus-time curve extrapolated to infinity according to the following equation:
		$AUC = AUC_{last} + \frac{C_{last}}{\lambda_z}$
		Values with a percentage of extrapolation > 20% will not be taken into account in the descriptive statistics
$t_{1/2z}$	olipudase alfa	Terminal half-life associated with the terminal slope (λ_z) determined according to the following equation:
		$t_{1/2z} = \frac{0.693}{\lambda_z}$
		where λ_z is the slope of the regression line of the terminal phase of the plasma concentration-versus-time curve, in semilogarithmic scale. Half-life is calculated by taking the regression of at least 3 points.
CL	olipudase alfa	Apparent total body clearance of a drug from the plasma calculated using the following equation:
		$CL = \frac{Dose}{AUC}$
V_{ss}	olipudase alfa	Apparent volume of distribution at steady state using the following equation:
		$V_{ss} = \frac{CL \times AUMC}{AUC}$

Note: The analyte and matrix for all PK parameters are olipudase alfa and plasma, respectively.

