6.1.1 Treatment period

Treatment Period

- During the treatment period, patients will receive an IV infusion of olipudase alfa every 2 weeks for 9 years or until olipudase alfa becomes commercially accessible (see maximum duration below), whichever comes first, unless the patient decides to enter another olipudase alfa clinical trial within the 9-year period prior to when olipudase alfa is commercially accessible.
- The term “commercially accessible” is defined as when olipudase alfa is commercially accessible to each patient on an individual basis (eg, reimbursement being in place). The duration of study treatment with olipudase alfa between local Regulatory approval and commercial accessibility should not exceed 90 days.
- Notwithstanding the above, every pediatric patient will be treated in the LTS13632 study for at least 3 years.
- The patient can switch immediately after the end of study treatment to commercial treatment without any gap in order to ensure continuity of treatment with olipudase alfa.

In the first 5 years, safety and efficacy assessments will occur at regular 3, 6, or 12 month intervals then only selected assessments will occur every 6 or 12 months after 5 years.

Schedule of Assessments

In the first 5 years, pharmacodynamic (PD) evaluations will occur every 3 months then every 6 months after the cutoff date for a planned second database lock of the study for purpose of regulatory submissions in 2021. After 5 years, PD evaluations will occur every 12 months.

PK evaluations will occur every 12 months only in the first 5 years and upon introduction of Process C(█) or Process C(█) at any time during the study. Beyond 5 years, pharmacokinetic testing will only occur upon the introduction of Process C(█) or Process C(█). For Process C(█), if treatment is not interrupted, PK sample collection will take place at the patient's last infusion under the current manufacturing scale and at the first infusion under Process C(█). For introduction of Process C(█), if treatment is not interrupted, PK sample collection will take place at the second infusion under Process C(█). In case reintroduction of olipudase alfa coincides with introduction of drug product from Process C(█) or Process C(█), PK samples will be collected at the infusion at which patients receive their usual dose of olipudase alfa under the new process. For schedule of PK assessment in adults, see [Section 1.6, Table 11](#).

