8.1.2 Route and method of administration

Patients will receive IV olipudase alfa over the same time period as in their original study. The length of the infusion time may be adjusted based on the patient's tolerance of the infusion.

During the study, pediatric patients who reach adult age (18 years old) will receive the adult infusion volume.

See [Section 8.1.5](#) for information on dose adjustments following dosing delays or missed doses.

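### Protocol Table 15 defines Vss by the bolus formula; for an infused drug it exceeds the true Vss by clearance times mean input time

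*Protocol*

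**What the plan says.** Protocol 9.3.8.3.3 introduces Table 15 with "The following PK parameters will be calculated using noncompartmental methods from plasma olipudase alfa concentrations". The Vss row reads "Apparent volume of distribution at steady state using the following equation", followed by CL × AUMC/AUC. AUMC is not defined. The AUClast row integrates from time zero, but the table does not say whether that is the start or the end of infusion. Tables 11 and 12 time the post-dose samples from the end of infusion. The integration method is given only as trapezoidal.

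The drug is infused: under Protocol 6.1.1, "patients will receive an IV infusion of olipudase alfa every 2 weeks". Protocol 8.1.2 gives no duration. It says "Patients will receive IV olipudase alfa over the same time period as in their original study" and adds "The length of the infusion time may be adjusted based on the patient's tolerance of the infusion". Protocol 8.6.1 foresees slowing or interrupting an infusion when a reaction occurs.

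Most of what a correction needs is collected. Protocol 9.3.8.3.1 says for adults: "The exact time of dose administration (start and stop times of infusion), rate of infusion, and dose will be recorded along with exact sampling times". The pediatric counterpart, 9.3.8.4.1, also lists the times of rate changes. Protocol 9.3.8.4.3 lets the Table 15 parameters be used for pediatric noncompartmental results. The SAP (2.1.6 and 2.4.9.2) mentions a volume only if applicable and gives no formula for it.

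**The concern.** Vss equals CL × MRT, where MRT describes disposition of the drug once it is in the body. After a bolus, AUMC/AUC is that MRT. After an infusion, AUMC/AUC also includes the average time at which drug entered the body. A formula without that term counts part of the infusion as distribution volume.

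What is at stake is limited but real. Vss is a named PK parameter, and characterising PK is a secondary objective. The excess depends on infusion length, so two infusions in the same patient with different durations give different values of Vss even if disposition is unchanged.

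**Working it through.** **Inputs.** From the documents: the Table 15 formula, the infusion route, the adjustable infusion time, and the Table 11 sampling times (pre-infusion, end of infusion, then 1, 4, 8, 24, 48 and 96 h). Assumed, because the documents give neither: infusion time T and MRT (or half-life). There is no figure in the plan to reproduce.

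**Formula.** With linear kinetics and time zero at infusion start, the concentration curve is the input convolved with the disposition function, so mean times add: AUMC/AUC = MRT + MIT. Then

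- printed formula: CL × (MRT + MIT) = Vss + CL × MIT;
- at constant rate, MIT = T/2, so the excess is CL × T/2;
- relative excess: (T/2)/MRT = T/(2 × MRT).

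**Size under assumed T and MRT.**

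| T | MRT 40 h | MRT 15 h |
|---|---|---|
| 1 h | 0.5/40 = 1.3% | 0.5/15 = 3.3% |
| 4 h | 2/40 = 5.0% | 2/15 = 13.3% |
| 6 h | 3/40 = 7.5% | 3/15 = 20.0% |

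**Check with exact integrals.**

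- One compartment, true Vss 10, half-life 24 h: CL = 10 × 0.693/24 = 0.289. A bolus gives 10.000. T = 4 h gives 10.578; the excess of 0.578 equals 0.289 × 2 (5.8%).
- Half-life 12 h, T = 4 h: 11.155 (11.6%).
- Two compartments, true Vss 7.0, terminal half-life about 17 h: 7.32, 7.64 and 7.96 at T = 2, 4 and 6 h (4.6%, 9.1%, 13.7%).
- Subtracting T/2 returned the true value in every case.
- Over a wider one-compartment grid (half-life 6 to 48 h, T = 1 to 6 h) the excess ran from 0.7% to 34.7%.

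**Check on the adult sampling times.** One compartment, true Vss 10; half-lives 6, 12, 24 and 36 h crossed with T = 2, 4 and 6 h (12 cases):

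| Half-life, T | Linear: printed / corrected | Linear-up/log-down: printed / corrected |
|---|---|---|
| 24 h, 4 h | 9.66 / 9.11 | 10.62 / 10.04 |
| 12 h, 4 h | 10.06 / 8.99 | 11.32 / 10.16 |

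With a plain linear trapezoid the printed formula is closer to 10 in 9 of 12 cases. With linear-up/log-down the corrected formula is closer in all 12. On the same data the two always differ by CL × T/2.

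**When the rate is not constant.** MIT is then the dose-weighted mean of entry times. As an illustration, two equal-length steps at rates 1:2 give (1 × 0.25T + 2 × 0.75T)/3 = 0.583T, and three at 1:3:6 give (1 × T/6 + 3 × T/2 + 6 × 5T/6)/10 = 0.667T. T/2 would undercorrect both.

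**The case against.** Four counter-arguments carry weight.

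- **The reported value may not be too high.** With sparse samples and a linear trapezoid, integration error pulls Vss down and can cancel or outweigh the excess. This stands as a fact about the net error. It does not rescue the formula: the offset comes from a separate error, changes with half-life and infusion length, and disappears under linear-up/log-down. The protocol and SAP also name PK software without saying how it treats infusion input. So the documents show that the printed definition is wrong, not that every reported Vss will be.
- **T/2 is not a general correction.** It holds at constant rate only, and the protocol foresees rate changes and interruptions. This stands, and the fix uses MIT instead.
- **Process comparisons are largely protected.** A reader might infer that comparisons across manufacturing processes are generally distorted. For the scale change, Protocol 9.3.8.3.1 samples the last infusion at the old scale and the first at the new one in the same patient; if duration is unchanged, the excess is nearly equal on both sides. Protocol 11.6.4 makes these comparisons optional and does not single out Vss. The distortion arises only where the sampled infusions differ in duration or rate pattern.
- **The reach is narrow.** Table 15 applies firmly only to the 5 adults; for the approximately 20 pediatric patients, modelling may replace noncompartmental analysis. This limits the consequence, not the error.

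A reader might also infer that infusion time varies with dose, so that dose-level summaries of Vss are confounded. The documents do not say so: they tie infusion time to the previous study and to tolerance.

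**Conclusion.** The Vss definition in Table 15 is wrong for an infused drug. Measured from infusion start, it exceeds the true Vss by CL × MIT, or CL × T/2 at constant rate, and nothing in the SAP corrects it. The 1% to 20% range rests wholly on the assumed T and MRT and on linear kinetics; the documents cannot fix the size, which could be negligible for short infusions and long residence times.

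The missing term does not touch CL, AUC, Cmax or half-life, and no primary safety result depends on Vss. This is a formula to correct before Vss is reported or compared, not a threat to the trial's conclusions.

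**What to change.** In Table 15 write Vss = CL × (AUMC/AUC − MIT), and repeat it in SAP 2.4.9.2. Define MIT as T/2 for a constant-rate infusion, with T the actual duration, and otherwise as the dose-weighted mean input time from the recorded rates and times. Define AUMC, set time zero at infusion start, and specify linear-up/log-down trapezoids. Apply this to adult results and to any pediatric noncompartmental results.

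No new samples or visits are needed. There are three costs. The adult section does not list times of rate changes, as the pediatric section does, so these may have to be taken from source records for any adult PK infusion that was slowed or interrupted. Any Vss already summarised for an earlier data cutoff would need recalculation. If another trapezoidal rule was used before, AUC and CL would also shift slightly, and the change should be stated.

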9.3.8.4 Pharmacokinetic sampling and parameters in pediatric patients

9.3.8.4.1 Sampling time in pediatric patients

Pharmacokinetic sampling will occur at the time points listed in [Section 1.3](#) through [Section 1.6](#). Specific time points are detailed in [Table 12](#) for each age group. To minimize the amount of blood drawn, post dose time points have been selected for sparse sampling of PK parameters.

If a patient receives only a partial infusion (eg, due to a safety concern), PK sampling will be repeated the next time the patient receives that dose. If a repeat is required, all PK time points will be repeated.

In adolescent patients, windows around PK blood samples are ± 10 minutes for collection times <8 hours and ± 3 hours for collection times ≥ 8 hours post infusion.

Depending on patient age, blood samples may be drawn for PK assessments using an indwelling catheter from an arm that is not used for olipudase alfa infusions. The exact time of olipudase alfa infusions (start and stop times of infusion), rate of infusion, time of infusion rate changes, and dose will be recorded along with exact sampling times.

9.3.8.4.2 Number of pharmacokinetic samples in pediatric patients

[Table 16](#) shows the approximate number of plasma samples by age cohort.

Table 16 - Approximate number of plasma samples by pediatric age cohort

Collection	Adolescent cohort	Child cohort	Infant/early child cohort
Yearly collection (5 years)	7	6	5
Change in manufacturing scale			
Last infusion on old scale	7	6	5
First infusion on new scale	7	6	5
Updated manufacturing process			
Second infusion on updated process	7	6	5
Total by patient	56	48	40

9.3.8.4.3 Pharmacokinetics parameters in pediatric patients

Plasma concentration-time data will be analyzed by noncompartmental methods, nonlinear mixed effects modeling or by population-based analysis, based upon patient age and data suitability. Where appropriate, PK parameters calculated using noncompartmental methods from plasma olipudase alfa concentrations may include those listed in [Table 15](#).

9.3.9 Pharmacodynamic assessments

Only patients who previously participated in the DFI13412 study will have PD assessments for clearance of sphingomyelin accumulation in liver tissue. All patients will be assessed for metabolite levels in plasma and/or DBS, as well as plasma ceramide.

9.3.9.1 Liver biopsy for sphingomyelin in liver tissue (only patients who previously participated in the DFI13412 study)

Liver biopsy samples will be evaluated for sphingomyelin accumulation and liver pathology in the patients who previously participated in the DFI13412 study who were at least 18 years old when they entered in the study. Patients who were younger than 18 years old when they entered the study will not have liver biopsies. See [Section 9.1.12](#) for details about liver biopsies.

9.3.9.2 Metabolite levels in plasma and dried blood spot (all patients)

Metabolite levels (eg, sphingomyelin, lyso-sphingomyelin) in plasma and/or DBS will be quantified by the sponsor (or designee) using samples collected as detailed in the study flow chart in [Section 1.1](#) through [Section 1.5](#). Procedure, preparation, and sample shipment guidelines for plasma and DBS sampling are provided in the corresponding manual.

9.3.9.3 Plasma ceramide (all patients)

Plasma ceramide will be quantified at the time points shown in the flow chart in [Section 1.1](#) through [Section 1.5](#). Plasma ceramide is also being tested as a safety biomarker.

9.4 APPROPRIATENESS OF MEASUREMENTS

The safety, efficacy, and PK/PD measurements in this trial are accepted methods for assessing patient safety and outcomes.

9.5 SAMPLED BLOOD VOLUME

For all pediatric patients, no more than 7 mL/kg of blood will be collected during any 8-week period. Additional blood samples may be collected at the investigator's discretion for patient safety monitoring.

If a PK or IgG sample collection for the planned introduction of drug product from Process C(█) was erroneously taken, the future sample collection will be adjusted according to the blood volume allowed per each age cohort in order to avoid excessive blood withdrawal. For specific details, please refer to Study Manual.

[Table 17](#) shows the approximate sampled blood volume in patients ages 12 to <18 years old in the first 5 years.

Table 17 - Approximate sampled blood volume in patients ages 12 to <18 years in the first 5 years

Assessment	Volume (mL) per sample	Number of samples per year	Total (mL) per year
Liver function, clinical chemistry, and lipid profile	5.0	4	20.0
Hematology	2.0	4	8.0
Coagulation	3.6	4	14.4
Safety biomarkers	6.5	4	26.0
Efficacy biomarkers	10.0	4	40.0
Serum bone-specific AP and C-telopeptide	2.5	4	10.0
Metabolites in plasma and/or DBS	3.2	4	12.8
Anti-olipudase alfa IgG and neutralizing antibodies in IgG-positive patients	3.5	4	14.0
Olipudase alfa pharmacokinetics	1.5	7	10.5
		Approximate total per year	155.7
		Approximate total per 5 years	778.5

AP=alkaline phosphatase

Table 18, Table 19 show the additional approximate sampled blood volume in patients ages 12 to <18 years old with an olipudase alfa manufacturing scale change or manufacturing process update respectively. Not all of the patients will be exposed to both changes; therefore, blood volume would be calculated individually. To avoid excessive blood volume withdrawn, if similar assessment is regularly scheduled (IgG, PK or hematology and coagulation) in the same month, priority is given to manufacturing scale or updated manufacturing process update assessments and the regular similar assessments may be canceled.

Table 18 - Additional approximate sampled blood volume in patients ages 12 to <18 years with an olipudase alfa manufacturing scale change

Assessment	Volume (mL) per sample	Number of samples	Total (mL)
Anti-olipudase alfa IgG and neutralizing antibodies in IgG-positive patients	3.5	1 sample per month for 6 months	21.0
Olipudase alfa pharmacokinetics - prior to manufacturing scale change	1.5	7	10.5
Olipudase alfa pharmacokinetics - post manufacturing scale change	1.5	7	10.5
Approximate additional volume per study			42.0

Table 19 - Additional approximate sampled blood volume in patients ages 12 to <18 years with the olipudase alfa updated manufacturing process

Assessment	Volume (mL) per sample	Number of samples	Total (mL)
Anti-olipudase alfa IgG and neutralizing antibodies in IgG-positive patients	3.5	1 sample per month for 6 months	21.0
Olipudase alfa pharmacokinetics – Second infusion on updated process	1.5	7	10.5
Hematology samples 3 months after first infusion on updated process	2	1	2
Coagulation and platelet samples 3 months after first infusion on updated process	3.6	1	3.6
Approximate additional volume per study			37.1

Table 20 shows the approximate sampled blood volume in patients ages 12 to <18 years old beyond 5 years.

Table 20 - Approximate sampled blood volume in patients ages 12 to <18 years beyond 5 years

Assessment	Volume (mL) per sample	Number of samples per year	Total (mL) per year
Liver function, clinical chemistry, and lipid profile	5	2	10.0
Hematology	3.6	2	7.2
Safety biomarkers	6.5	2	13.0
Efficacy biomarkers	10	1	10.0
Metabolites in plasma and/or DBS	3.2	1	3.2

Assessment	Volume (mL) per sample	Number of samples per year	Total (mL) per year
Approximate total per year, beyond 5 years			43.4
Approximate total per 4 years, beyond 5 years			173.6

Table 21 shows the approximate sampled blood volume in the child cohort (6 to <12 years old) and in patients ages 3 to <6 years old in the first 5 years.

Table 21 - Approximate sampled blood volume in patients in the child cohort (6 to <12 years) and in patients ages 3 to <6 years in the first 5 years

Assessment	Volume (mL) per sample	Number of samples per year	Total (mL) per year
Liver function, clinical chemistry, and lipid profile	4.0	4	16.0
Hematology	1.2	4	4.8
Coagulation	2.8	4	11.2
Safety biomarkers	6.2	4	24.8
Efficacy biomarkers	5.1	4	20.4
Serum bone-specific AP and C-telopeptide	2.2	4	8.8
Metabolites in plasma and/or DBS	1.5	4	6.0
Anti-olipudase alfa IgG and neutralizing antibodies in IgG-positive patients	1.1	4	4.4
Olipudase alfa pharmacokinetics	1.5	6	9.0
		Approximate total per year	105.4
		Approximate total per 5 years	527.0

AP=alkaline phosphatase

Table 22 and **Table 23** show the additional approximate sampled blood volume in patients in the child cohort (6 to <12 years) and ages 3 to <6 years with an olipudase alfa manufacturing scale change to Process C(█) or manufacturing process update to Process C(█) respectively. Not all of the patients will be exposed to both changes; therefore blood volume would be calculated individually. To avoid excessive blood volume withdrawn, if similar assessment is regularly scheduled (IgG, PK or hematology and coagulation) in the same month, priority is given to manufacturing scale or updated manufacturing process update assessments and the regular assessment may be canceled.

Table 22 - Additional approximate sampled blood volume in patients in the child cohort (6 to <12 years) and ages 3 to <6 years with an olipudase alfa manufacturing scale change

Assessment	Volume (mL) per sample	Number of samples	Total (mL)
Anti-olipudase alfa IgG and neutralizing antibodies in IgG positive patients	2.2	1 sample per month for 6 months	13.2
Olipudase alfa pharmacokinetics – prior to manufacturing scale change	1.5	6	9.0
Olipudase alfa pharmacokinetics – post manufacturing scale change	1.5	6	9.0
Approximate additional volume per study			31.2

Table 23 - Additional approximate sampled blood volume in patients in the child cohort (6 to <12 years) and ages 3 to <6 years with an olipudase alfa manufacturing process update

Assessment	Volume (mL) per sample	Number of samples	Total (mL)
Anti-olipudase alfa IgG and neutralizing antibodies in IgG-positive patients	2.2	1 sample per month for 6 months	13.2
Olipudase alfa pharmacokinetics – Second infusion on updated process	1.5	6	9.0
Hematology samples 3 months after first infusion on updated process	1.2	1	1.2
Coagulation and platelet samples 3 months after first infusion on updated process	2.8	1	2.8
Approximate additional volume per study			26.2

Table 24 shows the approximate sampled blood volume in the child cohort (6 to <12 years old) and in patients ages 3 to <6 years old beyond 5 years.

Table 24 - Approximate sampled blood volume in patients in the child cohort (6 to <12 years) and in patients ages 3 to <6 years - beyond 5 years

Assessment	Volume (mL) per sample	Number of samples per year	Total (mL) per year
Liver function, clinical chemistry, and lipid profile	4	2	8.0
Hematology	2.8	2	5.6
Safety biomarkers	6.2	2	12.4
Efficacy biomarkers	5.1	1	5.1
Metabolites in plasma and/or DBS	1.5	1	1.5

Assessment	Volume (mL) per sample	Number of samples per year	Total (mL) per year
Approximate total per year, beyond 5 years			32.6
Approximate total per 4 years, beyond 5 years			130.4

Table 25 shows the approximate sampled blood volume in patients from birth to ≤ 2 years old in the first 5 years.

Table 25 - Approximate sampled blood volume in patients from birth to ≤ 2 years of age in the first 5 years

Assessment	Volume (mL) per sample	Number of samples per year	Total (mL) per year
Liver function, clinical chemistry, and lipid profile	4.0	4	16.0
Hematology	1.2	4	4.8
Coagulation	2.8	4	11.2
Safety biomarkers	4.0	4	16.0
Efficacy biomarkers	3.7	4	14.8
Serum bone-specific AP and C-telopeptide	2.2	4	8.8
Metabolites in plasma and/or DBS	1.5	4	6.0
Anti-olipudase alfa IgG and neutralizing antibodies in IgG-positive patients	1.1	4	4.4
Olipudase alfa pharmacokinetics	1.5	5	7.5
		Approximate total per year	89.5
		Approximate total per 5 years	447.5

AP=alkaline phosphatase

Table 26 and **Table 27** show the additional approximate sampled blood volume in patients from birth to ≤ 2 years of age with an olipudase alfa manufacturing scale change or manufacturing process update respectively. Not all of the patients will be exposed to both changes; therefore blood volume would be calculated individually. To avoid excessive blood volume withdrawn, if similar assessment is regularly scheduled (IgG, PK or hematology and coagulation) in the same month, priority is given to manufacturing scale or updated manufacturing process update assessments and the regular assessment may be canceled.

Table 26 - Additional approximate sampled blood volume in patients from birth to ≤ 2 years of age with an olipudase alfa manufacturing scale change

Assessment	Volume (mL) per sample	Number of samples	Total (mL)
Anti-olipudase alfa IgG and neutralizing antibodies in IgG-positive patients	1.1	1 sample per month for 6 months	6.6
Olipudase alfa pharmacokinetics – prior to manufacturing scale change	1.5	5	7.5
Olipudase alfa pharmacokinetics – post manufacturing scale change	1.5	5	7.5
Approximate additional volume per study			21.6

Table 27 - Additional approximate sampled blood volume in patients from birth to ≤ 2 years of age with an olipudase alfa manufacturing process update

Assessment	Volume (mL) per sample	Number of samples	Total (mL)
Anti-olipudase alfa IgG and neutralizing antibodies in IgG-positive patients	1.1	1 sample per month for 6 months	6.6
Olipudase alfa pharmacokinetics – Second infusion on updated process	1.5	5	7.5
Hematology samples 3 months after first infusion on updated process	1.2	1	1.2
Coagulation and platelet samples 3 months after first infusion on updated process	2.8	1	2.8
Approximate additional volume per study			18.1

Table 28 shows the approximate sampled blood volume in patients from birth to ≤ 2 years old beyond 5 years.

Table 28 - Approximate sampled blood volume in patients from birth to ≤ 2 years of age- beyond 5 years

Assessment	Volume (mL) per sample	Number of samples per year	Total (mL) per year
Liver function, clinical chemistry, and lipid profile	4	2	8
Hematology	2.8	2	5.6
Safety biomarkers	4	2	8
Efficacy biomarkers	3.7	1	3.7
Metabolites in plasma and/or DBS	1.5	1	1.5

Assessment	Volume (mL) per sample	Number of samples per year	Total (mL) per year
Approximate total per year, beyond 5 years			26.8
Approximate total per 4 years, beyond 5 years			107.2

Additional blood samples may be required for IgE, serum tryptase, and complement activation following moderate, severe, or recurrent mild IARs suggestive of hypersensitivity reactions. Additional blood volumes are provided in [Table 29](#).

Table 29 - Approximate sampled blood volume per infusion following moderate, severe, or recurrent IARs suggestive of hypersensitivity reactions

Type	Volume (mL) per sample
IgE antibodies	3.5
Serum tryptase	3.5
Complement	2.0
Total per infusion	9.0

